#### Sample Size for Phase 3b

The primary safety endpoints will be evaluated in the Phase 3b SAS and the Phase 3b RAS. With a sample size of ~16,000 participants randomized and with approximately 8,000 participants randomized in the study to receive ARCT-154 for the primary safety analysis, if the incidence rate of an adverse event is 0.1%, the probability to detect one event in 8,000 vaccinated participants is >99.9%, based upon the following formula:

$$p = 1 - (1 - R)^N$$

where R = incidence rate and N = sample size

For the overall primary efficacy objective of the study, the null hypothesis is that the vaccine efficacy (VE) of ARCT-154 to prevent first occurrence of polymerase chain reaction (PCR)-confirmed COVID-19 is  $\leq 30\%$  (ie,  $H_0^{\text{efficacy}}$ : VE  $\leq 0.3$ ).

The primary efficacy objective will be met if the lower limit of the 95% CI for VE exceeds 30%.

VE is defined as the percent reduction in the hazard of the primary endpoint (ARCT-154 versus placebo). Equivalently, the null hypothesis is as follows:

- $H_0^{\text{efficacy}}$ : HR > 0.7 (equivalently, proportional hazards VE  $\leq 0.3$ )

A Cox proportional hazard model will be used to assess the magnitude of the study group difference (ie, HR) between ARCT-154 and placebo at a 1-sided 0.025 significance level.

Under the assumption of proportional hazards over time and with 1:1 randomization of ARCT-154 and placebo, a total of 372 COVID-19 cases will provide approximately 90% power to detect a 50% reduction in hazard rate (50% VE), rejecting the null hypothesis with a 1-sided false positive error rate of 0.025.

The study will be considered positive at the primary analysis if the one-sided p-value for rejecting HR  $\geq 0.7$  is less than or equal to 0.025.

### Sample Size for Phase 3c Substudy

The primary safety endpoints of Phase 3c will be conducted in the Phase 3c Safety Analysis Set and Phase 3c Reactogenicity Analysis Set. With a sample size of approximately 2,400 participants randomized and with approximately 1,200 participants randomized in the study to receive ARCT-154 or ChAdOx1 for the safety analysis, based upon the following formula, if the incidence rate of an adverse event is 0.1%, the probability to detect one event in 1,200 vaccinated participants is 69.9% and if the incidence rate is 1.0% the probability is more than 99%:

$$p = 1 - (1 - R)^N$$

where R = incidence rate and N = sample size

## 6.2 General Statistical Methods

### 6.2.1 General Methods

All outputs will be incorporated into RTF files, sorted and labeled according to the International Conference on Harmonization (ICH) recommendations, and formatted to the appropriate page size(s).

Tabulations will be produced for appropriate demographic, baseline, efficacy, immunogenicity and safety parameters. For categorical variables, summary tabulations of the number and percentage within each category (with a category for missing data) of the parameter will be presented. For continuous variables, the mean, median, standard deviation, 1st and 3rd quartiles, minimum and maximum values will be presented. All percentages will be presented to one decimal place. Two-sided 95% confidence intervals will be produced where applicable, unless otherwise stated.

## 6.2.2 Definition of Baseline

Baseline is defined as the last non-missing assessment prior to the first dose of study vaccine administration. If an assessment is collected on the day of first dose of study vaccine administration and time of the dose or assessment is not available, such assessment will be considered for the derivation of baseline. Assessments labeled as 30 minutes post-dose and 3 hours post-dose will not be considered for the baseline derivation, even if the time is not available.

## 6.2.3 Statistical Hypothesis

### Phase 1/2/3a Substudy Statistical Hypothesis

As per protocol, the primary immunogenicity objective (assessment of ARCT NAb responses by surrogate virus neutralization test (sVNT) at Day 57 versus Placebo) was to be assessed by means of the following Hypotheses:

- Null hypothesis ( $H_0^{\text{Immunogenicity}}$ ): lower bound of the 95% CI of ARCT-154 seroconversion rate at Day 57 ( $SC^{154}$ )  $\leq$  Placebo seroconversion rate at Day 57 ( $SC^{\text{Placebo}}$ ); i.e.,  $H_0^{\text{Immunogenicity}}$ : lower bound 95% CI for  $SC^{154} \leq SC^{\text{Placebo}}$  versus,
- Alternative hypothesis ( $H_1^{\text{Immunogenicity}}$ ): lower bound of the 95% CI of  $SC^{154} > SC^{\text{Placebo}}$

Phase 1/2/3a part of the study was to be considered to meet its primary immunogenicity objective if the lower bound of the 95%CI for  $SC^{154} > SC^{\text{Placebo}}$ . Following regulatory interactions, a more conservative methodology has been added:

- $H_0^{\text{Immunogenicity}}$ : lower bound of the 95% CI of  $(SC^{154}-SC^{\text{Placebo}}) \leq 0\%$  , versus
- $H_1^{\text{Immunogenicity}}$ : lower bound of the 95% CI of  $(SC^{154}-SC^{\text{Placebo}}) > 0\%$

The 95% CI for the difference of seroconversion rates at Day 57 between the two groups (ARCT-Placebo) will be calculated using the Miettinen and Nurminen method. Two-sided  $\alpha = 0.05$  will be used for all tests

There is no hypothesis testing for safety data analysis. Where statistical methods are applied, the emphasis will be on estimation with 95% CIs.

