8.5.1 Sample Size for Phase 1/2/3a Substudy

Data from Phases 1, 2 and 3a will be pooled up to Day 92 for safety analyses, which will be performed in the Phase 1/2/3a SAS and Phase 1/2/3a RAS (Section 8.2). The total sample size for Phase 1/2/3a is primarily driven by the size of safety database required at the time of potential EUA application. With approximately 750 participants randomized in Phases 1, 2 and 3a to receive ARCT-154 for the Phase 1/2/3a primary safety analysis, if the incidence rate of an adverse event is 1.0%, the probability to detect one event in 750 vaccinated participants is >99%, based upon the following formula:

$$p = 1 - (1 - R)^N$$

where R = incidence rate and N = sample size

Data from Phases 1, 2 and 3a will be pooled up to Day 92 for immunogenicity analyses, which will be performed in the Phase 1/2/3a IAS (Section 8.2). The primary immunogenicity endpoint is defined as the proportion of participants in each study vaccine group that demonstrate seroconversion (defined as: 4-fold increase in titer from baseline) by surrogate virus NAb assay at Day 57. Sensitivity analyses will be performed in the Phase 1/2/3a per protocol (PP) set.

The null hypothesis is $H_0^{\text{Immunogenicity}}$: lower bound 95% CI for $SC^{154} \leq SC^{\text{Placebo}}$. A sample size of 750 and 250 participants in the ARCT-154 and placebo groups respectively will provide greater than 90% power to exclude the null hypothesis with a 1-sided type 1 error rate of 0.025 assuming that 10% of participants are excluded from the analysis (for example due to baseline seropositivity), and that $SC^{154} > 50\%$ and $SC^{\text{Placebo}} \leq 10\%$.

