## 2.2 Randomization Methodology

Phase 1, 2 and 3a participants were randomly assigned 3:1 (ARCT-154:placebo), while Phase 3b participants were randomly assigned 1:1 (ARCT-154:placebo).

- Participants in Phase 1 and 3b received two doses of one type of study vaccine on Day 1 and 29 (ARCT 154 or placebo) and then two doses of the opposite vaccine (placebo or ARCT-154) on Day 92 and 120 (referred to as ‘Switchover’).
- Participants in Phase 2/3a who received ARCT-154 in the initial two-dose vaccination series were further randomized via IVRS to receive either ARCT-154 or placebo (in a 3:1 ratio) at Day 92 followed by placebo at Day 120 (referred to as “Re-randomization”). Participants that received placebo in the initial vaccination series underwent Switchover to receive ARCT-154 at Day 92 and Day 120 (referred to as “Switchover”).

Phase 3c participants were randomized 1:1 to receive ARCT-154 or ChAdOx1; no Switchover or re-randomization occurred for Phase 3c participants as all participants in this cohort receive active vaccine.

For Phases 2, 3a, 3b and 3c, prior to randomization, participants were stratified by the following 3 stratification factors:

- Age < 60 at high risk of severe COVID-19
- Age < 60 not at high risk of severe COVID-19
- Age ≥ 60 years of age (considered at risk of severe COVID-19 by default)

Participants were defined as “at risk” if they are 60 years of age or older OR have medical history described as putting an individual at risk or possibly at risk of severe coronavirus disease 2019 (COVID 19).

As the eligibility criteria for Phase 1 exclude participants ≥ 60 years of age or otherwise at risk for severe COVID-19, stratification did not occur for Phase 1.

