#### Sample Size for Phase 1/2/3a Substudy

Data from Phases 1, 2 and 3a will be pooled up to Day 92 for safety analyses, which will be performed in the Phase 1/2/3a SAS and Phase 1/2/3a RAS. The total sample size for Phase 1/2/3a is primarily driven by the size of safety database required at the time of potential EUA application. With approximately 750 participants randomized in Phases 1, 2 and 3a to receive ARCT-154 for the Phase 1/2/3a primary safety analysis, if the incidence rate of an adverse event is 1.0%, the probability to detect one event in 750 vaccinated participants is >99%, based upon the following formula:

$$p = 1 - (1 - R)^N$$

where R = incidence rate and N = sample size

Data from Phases 1, 2 and 3a will be pooled up to Day 92 for immunogenicity analyses, which will be performed in the Phase 1/2/3a IAS. The primary immunogenicity endpoint is defined as the proportion of participants in each study vaccine group that demonstrate seroconversion (defined as: 4-fold increase in titer from baseline) by surrogate virus NAb assay at Day 57.

The null hypothesis is  $H_0^{\text{Immunogenicity}}$ : lower bound 95% CI for  $SC^{154} \leq SC^{\text{Placebo}}$ . A sample size of 750 and 250 participants in the ARCT-154 and placebo groups respectively will provide greater than 90% power to exclude the null hypothesis with a 1-sided type 1 error rate of 0.025 assuming that 10% of participants are excluded from the analysis (for example due to baseline seropositivity), and that  $SC^{154} > 50\%$  and  $SC^{\text{Placebo}} \leq 10\%$ . However, a more conservative hypothesis testing has been added (refer to section 6.2.3 for more details).

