#### 6.4.1 Primary Efficacy Analysis

The analysis of the first primary endpoint will consider the first occurrence of confirmed, protocol-defined COVID-19 with onset between Day 36 and Day 92 inclusive.

Time at risk = [Last date at risk – (Date received 2nd dose + 7 days)]+1; where the last date at risk will be defined as COVID-19-event date or censor date, whichever comes first.

Summaries of vaccine efficacy will display the number of participants included in the analysis, number of protocol-defined COVID-19 cases (Protocol Appendix 2) and surveillance time in person-year will be summarized in each vaccine group. Surveillance time refers to the total person-time at risk (years) for the given endpoint.

The vaccine efficacy (VE) is defined as the percent reduction in the hazard rate of the COVID-19 events (ARCT-154 versus placebo). The vaccine efficacy is calculated as:

$$VE = 1 - \frac{h_{ARCT-154}}{h_{placebo}} = 1 - HR$$

where  $h_{ARCT-154}$  and  $h_{placebo}$  are hazard rates of the confirmed, protocol-defined COVID-19/Severe COVID-19/death among those in ARCT-154 group and placebo group, respectively.

Vaccine efficacy will be displayed together with 95% confidence interval (CI). Vaccine efficacy is calculated from 1-hazard ratio, where, the hazard ratio (HR) and 95% CI are measured by adjusted Cox proportional hazard regression, with the assumptions of proportional hazards over time. The p-value will be calculated from Cox proportional hazard regression.

Efficacy summaries will also include the proportion of participants with COVID-19 cases in each vaccine group will be displayed together with the Clopper-Pearson 95% CI and a comparison between ARCT-154 and Placebo with 95% CIs. A Log-Rank test p-value will be calculated (in addition to VE% Cox model p-value).

Factors to be used as covariates in Cox proportional hazard regression include:

- Risk group: A randomization stratification factor for age and health risk for severe disease;  $\geq 18$  to  $< 60$  years and “healthy”,  $\geq 18$  and  $< 60$  years and “at risk” and  $\geq 60$  years. Age and health risk at randomization collected in the CRF will be used.
- Study site region: Study site is a randomization stratification factor. However, the sites are grouped into study site region for adjustment factor. Site collected in the CRF will be used.
  - Risk group or study site region will be removed from the model when performing subgroup analysis on that variable.

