- GMC (or GMT) ratio of ARCT-154 versus placebo and corresponding 95% CI by timepoint (not applicable for three dose-schedule analysis)
- Geometric Mean Fold Rise (GMFR) and corresponding 95% CI at each timepoint, from Day 1 (and additionally from Day 92 for Day 120 where applicable) by treatment arm.

Reverse cumulative functions will be presented for each assay by treatment arm and post baseline timepoint. Antibody levels will be presented on x axis in log10 scale.

Geometric mean concentration (GMC) is the geometric mean of the antibody concentration and is derived as follows:

$$GMC = \ln^{-1} \left( \frac{\sum_{i=1}^n \ln X_i}{n} \right), \text{ where } X: \text{antibody concentration}$$

The GMC ratio at timepoint D is the ratio of ARTC-154 GMC obtained at timepoint D over placebo GMC obtained at timepoint D.

$$\text{GMC ratio at Day D} = \frac{\text{ARTC-154 GMC at Day D}}{\text{Placebo GMC Day D}}$$

GMFR is defined as the geometric mean of fold rise of post-study intervention concentrations over the Day 1 (baseline) concentration. These will be calculated as follows:

$$GMFR = \ln^{-1} \left( \frac{\sum_{i=1}^n \ln \left( \frac{X_2}{X_1} \right)}{n} \right),$$

where X2 is the antibody concentration at time point of evaluation and X1 is the antibody concentration at baseline (or Day 92).

Handling of immune response concentration below LLOQ or greater than ULOQ is described in section 5.2.

Conversion factors to be applied to immunogenicity parameters are summarized in section 9.4.

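### The Phase 1/2/3a ARCT-154/placebo GMC ratio uses neither the randomisation risk group nor the Day 1 concentration; an adjusted ratio is a small, nearly free improvement

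*SAP*

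**What the plan says.** **Randomisation.** SAP section 2.2 states: "For Phases 2, 3a, 3b and 3c, prior to randomization, participants were stratified by the following 3 stratification factors". The three levels are under 60 at high risk, under 60 not at high risk, and 60 or over. Phase 1 was not stratified. The same section gives the allocation: "Phase 1, 2 and 3a participants were randomly assigned 3:1 (ARCT-154:placebo"). Planned enrolment (protocol section 4.1) is 100 + 300 + 600, so 900 of 1,000 Phase 1/2/3a participants were randomised within strata.

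**GMC ratio.** SAP section 6.5 lists the "GMC (or GMT) ratio of ARCT-154 versus placebo and corresponding 95% CI by timepoint". Its formula is the ARCT-154 GMC at a given day over the placebo GMC at that day. There is no covariate, and the section does not say how the interval is computed.

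**Baseline data.** Protocol section 4.5.5.3 has a Day 1 sample for antibody response from every Phase 1/2/3a participant. SAP appendix 9.3 lists Day 1 for every assay in each phase tested.

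**Contrast.** SAP section 6.4.1 puts risk group in the efficacy Cox model, describing it so: "Risk group: A randomization stratification factor for age and health risk for severe disease".

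**Seroconversion.** SAP section 6.2.3 says the 95% interval for the Day 57 difference "between the two groups (ARCT-Placebo) will be calculated using the Miettinen and Nurminen method". No stratum term is named there or in section 6.5.2.

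**The concern.** The plan adjusts for the randomisation factor in one analysis and gives no reason for leaving it out of the antibody comparison. For a log-transformed antibody level, the participant's own Day 1 value and age/risk group are natural predictors of the Day 57 value. A crude ratio leaves their contribution in the residual variance. It also leaves any chance imbalance in baseline antibody, and in age or risk within the unstratified Phase 1, in the estimate. What is at stake is some precision and consistency with the efficacy analysis, not a pass/fail decision.

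**Working it through.** **1. The plan's own figure.** SAP section 6.1 states "A sample size of 750 and 250 participants in the ARCT-154 and placebo groups respectively will provide greater than 90% power", "with a 1-sided type 1 error rate of 0.025 assuming that 10% of participants are excluded from the analysis". The planning rates are above 50% and at most 10%. After 10% exclusions, 675 and 225 remain. SE of the difference = sqrt(0.50 × 0.50/675 + 0.10 × 0.90/225) = 0.0278. The difference of 0.40 is 14.4 standard errors, so power exceeds 99.9%. The stated figure is reproduced with a wide margin.

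**2. GMC ratio, covariates equally predictive in both arms.** On the log scale, crude SE = SD × sqrt(1/675 + 1/225) = 0.0770 × SD. Adjustment multiplies it by sqrt(1 − R²). The documents give neither SD nor R² for this contrast; both are assumptions.

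| R² (assumed) | Width factor | 95% CI multiplier, log-SD 1.0 (assumed) |
|---|---|---|
| 0 | 1.000 | 1.163 |
| 2% | 0.990 | 1.161 |
| 5% | 0.975 | 1.158 |
| 10% | 0.949 | 1.154 |
| 25% | 0.866 | 1.140 |

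**3. GMC ratio, covariates predictive only under ARCT-154.** Placebo recipients without infection may show little spread. Write V for the ARCT-154 log variance, of which a share R² is explained, with zero slope under placebo.
- With covariates centred and interacted with arm, the variance changes by R²V(1/900 − 1/675) = −R²V/2700.
- With one common slope, the fitted slope is about 675/900 = 0.75 of the ARCT-154 slope. The variance changes by R²V[(0.25² − 1)/675 + 0.75²/225] = +0.75 R²V/675.

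At R² = 10%:
- Placebo variance equal to V: crude variance is V(1/675 + 1/225) = 4V/675. The width factor is sqrt(1 − 0.10 × 0.0625) = 0.997 with interaction and sqrt(1 + 0.10 × 0.1875) = 1.009 with a common slope.
- Placebo variance near zero: crude variance is V/675. The factors are sqrt(1 − 0.10 × 0.25) = 0.987 and sqrt(1 + 0.10 × 0.75) = 1.037.

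A simulation at 675:225 agreed to within about 0.5 percentage points. The common-slope model can therefore lose precision under 3:1 allocation, while the interacted model does not.

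**4. Seroconversion, crude against stratified Miettinen-Nurminen** (Mantel-Haenszel weights, 675:225, placebo 10% throughout; strata mix 60/20/20% and ARCT-154 rates assumed).

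| ARCT-154 rates by stratum | Crude | Stratified | Width ratio |
|---|---|---|---|
| 60/45/25% | 0.3417 to 0.4513 | 0.3406 to 0.4531 | 1.027 |
| 55/50/35% | 0.3417 to 0.4513 | 0.3413 to 0.4520 | 1.010 |

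The stratified interval is slightly wider because the score variance imposes a common risk difference, which these scenarios violate. With a common difference of 0.40 (mix 50/30/20%), the ratios were 0.992 and 0.994. A within-stratum Wald variance gives SE ratios of 0.982 and 0.994 in the two tabulated scenarios, but that is a different method.

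**The case against.** **Nothing turns on it.** The GMC ratio has no margin, and SAP section 6.5 computes no p-values. The only GMC ratio with a margin was Phase 3c noninferiority, which section 7.1 drops. This stands, and it limits the point to an efficiency improvement.

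**Baseline may explain little.** The IAS removes anyone with a positive test or anti-nucleocapsid seropositivity up to Day 57, values below LLOQ are set to LLOQ/2, and GMFR already reports change from Day 1. This is a fair inference and keeps the plausible R² low. It is not complete: the final SAP no longer uses baseline neutralising antibody to define early infection, so baseline titre may still vary, and age/risk remains available.

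**Risk group is already examined.** Section 6.5.7 repeats the seroconversion rates by subgroup. Those outputs give rates within groups, not an adjusted overall GMC ratio. SAP Part 1's stratified Cochran-Mantel-Haenszel analysis was dropped because significance testing against placebo was judged clinically uninformative (section 7.3). That is an argument against p-values, not against an adjusted estimate.

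**Late change.** Some SAP authors had access to unblinded participant-level Phase 1/2/3a data (section 2.4). This is a good reason to add the analysis rather than replace anything primary.

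**A stronger reading.** A reader might infer that the primary seroconversion interval is also wider than it need be, or that it ignores baseline titre. The documents do not support either. Seroconversion is a fourfold rise from each participant's own Day 1 value, and step 4 shows that stratifying the Miettinen-Nurminen interval does not reliably narrow it.

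**Conclusion.** The point holds for the GMC ratio only, as a minor improvement. The crude ratio leaves out a stratification factor and a baseline measurement that are both to hand. The expected gain is about 2.5% to 5% in log-scale width if the covariates explain an assumed 5% to 10% of variance in both arms. If placebo concentrations do not vary with the covariates, the gain at R² = 10% falls to between 0.3% and 1.3% with arm interactions, and a common-slope model gives no gain. No R² or SD in the documents narrows this range.

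For seroconversion, the unstratified Miettinen-Nurminen interval should stay primary. At the planning rates its lower limit is near 0.34 against a criterion of 0, and stratifying moves it by about 0.001 in the tabulated scenarios.

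**What to change.** - **SAP section 6.5:** add an adjusted GMC ratio from a linear model of log concentration on arm, risk group and log Day 1 concentration, with Phase 1 placed in the under-60 healthy group. Use heteroscedasticity-robust standard errors. Preferably centre the covariates and interact them with arm, because allocation is 3:1 and placebo variance may be small. The standard error should allow for the covariate means being estimated. Keep the crude ratio as descriptive, state how its interval is computed, and record that the adjusted analysis was added after Phase 1/2/3a unblinding.
- **SAP sections 6.2.3 and 6.5.2:** leave the primary seroconversion interval as it is. A risk-group-weighted difference with its own within-stratum variance may be added as a sensitivity analysis, with the weights and Phase 1's placement stated.
- **SAP sections 2.2 and 6.4.1:** reconcile them. The latter calls study site a randomisation stratification factor; the former, like protocol section 4.5.2, lists only the age/risk levels. Settle this before fixing any covariate list.

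The cost is SAP text and a few lines of code, with no new data.

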### Phase 3b Statistical Hypothesis

The overall primary endpoints for the study are evaluated in the Phase 3b population as follows:

- The overall primary efficacy endpoint for the study is vaccine efficacy as evaluated in the Phase 3b Modified Intent to Treat (mITT) population
- The overall primary safety endpoints are those evaluated in the Phase 3b Safety Analysis Set (SAS) and Phase 3b Reactogenicity Analysis Set (RAS)

There is no hypothesis testing for safety data analysis. Where statistical methods are applied, the emphasis will be on estimation with 95% CIs.

The primary statistical analyses for VE will be performed using virologically confirmed COVID-19 cases as adjudicated in a blinded fashion by the Independent Adjudication Committee.

The null hypothesis ( $H_0^{\text{Efficacy}}$ ) as follows:  $H_0^{\text{Efficacy}}: \text{VE} \leq 30\%$

VE is estimated as 1-HR, where HR is the hazard ratio, and will be presented together with 95% CIs. The primary efficacy objective will be met if the lower limit of the 95% CI for VE exceeds 30% in the Phase 3b mITT population.

Under the assumptions of proportional hazards over time and a 50% reduction in hazard rate (50% VE) and with 1:1 randomization of ARCT-154 and placebo, a total of 372 confirmed COVID-19 cases will provide approximately 90% power to reject the null hypothesis ( $H_0: \text{VE} \leq 30\%$ ), using a log-rank test statistic with a 1-sided false positive error rate of 0.025.

The secondary efficacy objectives (and second primary objective for regulatory filings outside of Vietnam) will be met if the lower limit of the 95% CI for VE exceeds 0%.

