#### **6.2.4 Multiple Comparisons/Multiplicity**

The overall primary efficacy objective for the study is determination of VE as evaluated in the Phase 3b mITT population. Hence the study will be regarded to have met the primary objective if the null hypothesis is rejected. Hence the primary efficacy objective will be met, and the study overall declared to be positive, if the lower limit of the 95% confidence interval (CI) for VE exceeds 30%. VE is defined as the percent reduction in the hazard of the primary endpoint (ARCT-154 versus placebo).

The overall key secondary objectives for the study are Phase 3b Secondary Endpoints 1 and 2. These endpoints will be evaluated in a hierarchical fashion such that Secondary Endpoint 1 will only be evaluated in a hypothesis testing fashion if the overall primary objective of the study has been met and Secondary Endpoint 2 will only be evaluated in a hypothesis testing fashion if the null hypothesis for Secondary Endpoint 1 has been rejected.

Phase 3b secondary endpoints 3 and 4 will be evaluated in a hypothesis generating fashion with any statistical significance being nominal.

For the pooled analyses, endpoints are nominally declared as primary/secondary/exploratory, but all endpoints are evaluated as sensitivity analyses to the equivalent endpoints being assessed in the Phase 3b populations.

Phase 1/2/3a and subgroups thereof constitute a distinct substudy with its own distinct objectives and endpoints. There is no testing procedure for controlling type 1 error for Phase 1/2/3a substudy primary or secondary endpoints. As this is a substudy, and there is no evaluation of

efficacy for this substudy, no adjustment of type 1 error is applied to the overall efficacy primary endpoint.

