### 7.3 Summary of changes from protocol documented in SAP Part 1 and SAP Part 2 not implemented in this SAP

The below table describes changes introduced in SAP Part 1 or SAP Part 2 that are not implemented in this SAP.

Protocol Section	Analysis method described originally in the protocol	Planned Analysis	Reasons of changes
Section 3.1 Phase 3b Primary Objectives and Endpoints	Single efficacy primary endpoint	
In SAP Part 2, it was specified that the first secondary endpoint for Phase 3b in the protocol (first occurrence of severe COVID-19) will be analyzed as a second primary endpoint.
 
In this SAP, first occurrence of severe COVID-19 will be analyzed as the first secondary endpoint for Phase 3b as specified in the protocol
	Regulatory feedback.
Section 3.4 Reactogenicity Analysis Set (RAS)	
Protocol: Includes all participants who receive a dose of study vaccine (ARCT-154 or placebo) prior to the specific window of observation (e.g., dose 1, dose 2) and who has returned at least a partially completed diary card reflecting that window of observation.
 
SAP Part1/2: the RAS includes all participants who receive a dose of study vaccine (ARCT-154 or placebo) prior to the specific window of observation (e.g., dose 1, dose 2) and who has returned at least a partially completed diary card reflecting that window of observation or have at least one reactogenicity report entered in the EDC for the 30 minute observation period after vaccination.
	
In this SAP, The RAS includes all participants who receive any dose of study vaccine (ARCT-154 or placebo or ChAdOx1) and provide at least 1 reactogenicity diary report.
	
The condition to receive a dose of study vaccine prior to the specific window of observation will not be implemented in the analysis set definition. Instead participants who did not receive a dose of study vaccine prior to the specific window of observation will not be included in the computation of the percentages in the specific window.

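### SAP 6.2.3 keeps a success rule for a withdrawn second primary objective and calls all secondaries met above 0%, which contradicts 6.2.4 for Secondary 3 and 4

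*SAP*

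**What the plan says.** SAP Section 6.2.3 (Phase 3b Statistical Hypothesis) sets the primary rule first: "The primary efficacy objective will be met if the lower limit of the 95% CI for VE exceeds 30"%. It closes with a second rule: "The secondary efficacy objectives (and second primary objective for regulatory filings outside of Vietnam) will be met if the lower limit" of the 95% interval for VE is above 0%. That sentence covers the secondaries as a group, adds a second primary objective, and states no condition on any earlier test.

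Three other places bear on it:

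- **Section 6.2.4 (Multiplicity)** tests Secondary 1 (severe COVID-19) only after the primary is met, and Secondary 2 only after Secondary 1 is rejected. For the rest: "Phase 3b secondary endpoints 3 and 4 will be evaluated in a hypothesis generating fashion with any statistical significance being nominal".
- **Section 7.3** records that SAP Part 2 had made severe COVID-19 a second primary, and reverses this after regulatory feedback: "In this SAP, first occurrence of severe COVID-19 will be analyzed as the first secondary endpoint for Phase 3b as specified in the protocol". Tables 2 and 6 also list it as Secondary 1.
- **Section 7.2** (the row on protocol Section 8.4.2) repeats the 0% rule for the secondary objectives, without the second-primary clause and without a gate.

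Section 6.4.1 still opens with "The analysis of the first primary endpoint will consider the first occurrence of confirmed, protocol-defined COVID-19", and 6.4.2.1 also refers back to a first primary endpoint.

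**The concern.** The parenthesis in 6.2.3 looks like a remnant of SAP Part 2: a success criterion for an objective that this SAP no longer has. The 0% sentence is written as a sufficient condition for every secondary, including two that 6.2.4 takes out of confirmatory testing.

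What is at stake is which efficacy claims count as confirmatory. Someone writing the study report from 6.2.3 could declare Secondary 3 (COVID-19 death) or Secondary 4 (regardless of baseline serostatus) met, and could present severe COVID-19 as a primary objective in filings outside Vietnam. Someone working from 6.2.4 could do neither. SAP Section 2.4 also records that some authors of this SAP had access to unblinded participant-level data from the earlier analyses. That is a further reason for endpoint status not to depend on which section is read.

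**Working it through.** **1. The plan's own figure.** The inputs from SAP 6.2.3 are the effect size and allocation, "a 50% reduction in hazard rate (50% VE) and with 1:1 randomization of ARCT-154 and placebo"; the error rate, "using a log-rank test statistic with a 1-sided false positive error rate of 0.025"; and the result claimed, "a total of 372 confirmed COVID-19 cases will provide approximately 90% power to reject the null hypothesis". The null hazard ratio is 0.7, so the ratio to detect is 0.5/0.7 = 0.714, with log −0.3365.

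- Schoenfeld: d = 4(1.960 + 1.282)² / 0.3365² = 372 after rounding up.
- Power at 372 events: Φ(0.3365 × √372/2 − 1.960) = 0.9006.
- The Freedman formula gives 379, within 3%.

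The sizing reproduces and is not in dispute.

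**2. The rules side by side.**

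| Endpoint | SAP 6.2.3 | Elsewhere in the SAP | Result |
|---|---|---|---|
| Primary | lower limit above 30% | 6.2.4: same | agree |
| Second primary | lower limit above 0% | 7.3: withdrawn; no table defines it | conflict |
| Secondary 1 | lower limit above 0% | 6.2.4: only after the primary is met | compatible; gate not cited |
| Secondary 2 | lower limit above 0% | 6.2.4: only after Secondary 1 | compatible; gate not cited |
| Secondary 3, 4 | lower limit above 0% | 6.2.4: nominal only | conflict |

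**3. What the literal rule would allow for Secondary 4.** This endpoint has the same case definition and window as the primary, and adds participants seropositive at baseline. The documents give no event count for it, so assume about 372. The standard error of the log hazard ratio is then about 2/√372 = 0.1037, and exp(−1.960 × 0.1037) = 0.816.

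- Observed VE needed for a lower limit above 30%: 1 − 0.7 × 0.816 = 42.9%.
- Observed VE needed for a lower limit above 0%: 1 − 0.816 = 18.4%.

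An observed VE between about 18% and 43% on both endpoints would miss the primary, yet under 6.2.3 taken alone Secondary 4 would be met.

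**4. Illustrative error rate for two ungated primaries.** Take each at one-sided 0.025 and exactly at its own null.

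- Independent: 1 − 0.975² = 0.0494.
- Simulation (500,000 draws) at assumed correlations 0.3, 0.5 and 0.8: 0.048, 0.045 and 0.039.
- Under the sequence in 6.2.4: 0.025.

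The documents state neither a familywise figure nor a correlation. Severe cases count in the primary endpoint (SAP 6.4), so positive correlation is expected.

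**The case against.** The best defence is a division of labour. Section 6.2.3 gives the null values and 6.2.4 gives the testing order, as protocol Sections 8.4.2 and 8.1 do. Section 7.2 says the 0% sentence was added to supply the hypothesis test for the secondary objectives, for which the protocol gave no null. For Secondary 1 and 2 this stands: the threshold is legitimate and only a cross-reference is missing. It does not help Secondary 3 and 4, which cannot be both met and nominal. Nor does it help the second-primary clause, which 7.3 retracts.

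The defence is also right about three stronger readings that a reader might infer:

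- **That the SAP permits a primary claim on severe COVID-19.** It does not. Section 1.2 points to one overall primary efficacy objective, 6.2.3 itself names one overall primary efficacy endpoint, 6.2.4 calls the study positive only on the 30% bound, and Tables 2 and 6 and Section 7.3 all make severe COVID-19 a secondary. One undefined parenthesis does not outweigh these.
- **That 6.2.3 cancels the hierarchy, so that error accumulates over the primary and all four secondaries.** Section 6.2.4 is intact. Such a sum would also need five independent tests, each at its null boundary. The endpoints share cases and the nulls differ (30% against 0%). If true VE were 0%, passing the 30% bound with 372 events would need z of about −5.4, a probability of about 3 in 10⁸.
- **That the 0% rule applies to the primary**, because Table 2 numbers efficacy as the second Phase 3b primary objective. Sections 6.2.3 and 6.2.4 both fix 30% for that endpoint.

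Finally, the case of a missed primary may be moot. Section 7.1 says clinical efficacy was demonstrated in Phase 3b, and Section 2.5 says the final analyses use the same endpoint data. That does not settle how Secondary 3, Secondary 4 and severe COVID-19 are to be labelled.

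**Conclusion.** The point holds as a contradictory decision rule. Section 6.2.3 conflicts outright with 7.3 on the second primary and with 6.2.4 on Secondary 3 and 4. For Secondary 1 and 2 it only omits the gate.

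The consequence concerns which claims are called confirmatory. No model, population, significance level or event count changes. The 4.9% figure is an illustration: it assumes that the parenthesis is acted on, that 6.2.4 is ignored, that both endpoints sit at their own nulls, and that the tests are independent. At assumed correlations of 0.3 to 0.8 it falls to between 4.8% and 3.9%, and under 6.2.4 the rate is 2.5%. This is worth correcting because the two sections give different answers. It does not undermine the primary analysis.

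**What to change.** - **SAP 6.2.3:** delete the parenthesis on a second primary objective and replace the sentence with: *Secondary 1 and Secondary 2 are each met when the lower 95% confidence limit for VE is above 0%, subject to the hierarchy in Section 6.2.4; Secondary 3 and 4 are nominal and are not declared met.*
- **SAP 7.2**, row on protocol Section 8.4.2: make the same change. Otherwise the unqualified 0% rule survives there.
- **SAP 6.4.1 and 6.4.2.1:** change *first primary endpoint* to *primary endpoint*.

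The cost is SAP wording only. No analysis or output has to be reprogrammed, and the 372-event sizing stands.
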